5.1.2 Primary Endpoint

The primary endpoint is Day +28 (4 weeks) following HCT for MM, with intervention arm patients followed for an additional 1-2 weeks until they are weaned from beta-blocker therapy.

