5.2 Sample Size and Power Calculation

We will enroll 40 participants undergoing autologous HCT for MM at MCW. Accounting for study attrition and beta-blocker intolerance, we aim to have 30 patients with a complete set of gene data. A sample size of 40 will inform our feasibility aim, while a targeted final sample of 15 participants in the intervention group will be sufficient for gene expression analysis. The gene expression sample size is based on previous studies with similar or smaller sample sizes that have evaluated gene expression as a function of psychosocial factors and yielded hundreds of differentially expressed genes that generate statistically significant results in higher-order bioinformatics.^{35, 45, 46} More specific sample size estimates are difficult to project with any greater accuracy, as there is not data on the effect size for gene expression differences as a function of propranolol in humans. To this end, the current proposal will inform future sample size estimations. This study is intended mainly to generate effect size estimates and 95% confidence intervals to aid with planning future research projects. We will generate both simple estimates of effect size as well as adjusted estimates, attempting to control for any accidental confounding that may occur despite randomization.

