5.3 Analysis of Primary Endpoints

5.3.1 Gene Expression Profiling

The final outcome for the gene expression analysis will be expression levels of the group of genes comprising the conserved transcriptional response to adversity (CTRA) profile. The CTRA profile represents a systemic shift in basal gene expression profiles among circulating immune cells during extended periods of stress, threat, or uncertainty consistent with the physiology of stress-associated illness.³²⁻³⁶ This profile is characterized by 53-genes and includes up-regulated expression of pro-inflammatory genes (*IL1A*, *IL1B*, *IL6*, *IL8*, *TNF*, *PTGS1*, *PTGS2*, *FOS*, *FOSB*, *FOSL1*, *FOSL2*, *JUN*, *JUNB*, *JUND*, *NFKB1*, *NFKB2*, *REL*, *RELA*, and *RELB*) and down-regulated expression of genes involved in type I interferon (IFN) responses (*GBP1*, *IFI16*, *IFI27*, *IFI27L1-2*, *IFI30*, *IFI35*, *IFI44*, *IFI44L*, *IFI6*, *IFIH1*, *IFIT1-3*, *IFIT5*, *IFIT1L*, *IFITM1-3*, *IFITM4P*,

IFITM5, IFNB1, IRF2, IRF7-8, MX1-2, OAS1-3, and OASL) and antibody synthesis (*IGJ, IGLL1, and IGLL3*).^{33, 34, 47, 48} This CTRA profile is significantly regulated through beta-adrenergic mediated signaling. The CTRA profile will include a composite of standardized scores on the 53 a priori defined genes and measured levels of each transcript treated as 53 repeated measurements analyzed by a mixed effect linear model with a residual covariance structure estimated to account for potential correlation among the 53 genes.

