Primary analyses will be performed at the time of all 3 blood draws (Baseline, Day -2, and Day +28) and will use general linear model analyses to quantify the association between expression of each of the 53 CTRA contrast genes and beta-blocker usage. To ensure analysis of patients with sufficient beta-blocker exposure, only gene expression data from study participants with an adherence rate of 80% (at either dose) will be used as comparators against the control group. Descriptive tables of patient-, disease-, and transplant-related factors will be prepared with separate columns by propranolol vs. no propranolol groups. Any demographic or psychosocial variables (other than those of primary interest) that are unevenly distributed between groups after randomization will be adjusted for in subsequent analyses as previously described using ANCOVA. Further, differences in gene expression will be compared between groups/variables that might not have been randomly distributed, regardless of beta-blocker treatment assignment, to ascertain whether these differences may be stronger than drug-attributed changes. The UCLA Social Genomics core will provide genetic and statistical analyses for gene expression data.

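### Section 5.3.1 does not say whether the pooled CTRA contrast or the 53 single-gene models decide the primary objective, and sets no false-discovery control for the gene-level results

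*Combined protocol and SAP*

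**What the plan says.** The opening paragraph of section 5.3.1 of the combined protocol and SAP points to a pooled outcome: "The final outcome for the gene expression analysis will be expression levels of the group of genes comprising the conserved transcriptional response to adversity". It fixes the gene set in advance ("This profile is characterized by 53-genes") and describes two ways of combining the genes. The first is a composite: "The CTRA profile will include a composite of standardized scores on the 53 a priori defined genes". The second is a single model with "measured levels of each transcript treated as 53 repeated measurements analyzed by a mixed effect linear model", in which the residual covariance allows for correlation among genes.

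The next paragraph of the same section gives the primary label to something else. "Primary analyses will be performed at the time of all 3 blood draws (Baseline, Day -2, and Day +28"), and these analyses "will use general linear model analyses to quantify the association between expression of each of the 53 CTRA contrast genes and beta-blocker usage". That is one treatment model per gene per draw.

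Section 5.1.2 names one time point: "The primary endpoint is Day +28 (4 weeks) following HCT for MM". Section 5.2 describes the study as mainly a source of effect sizes and 95% confidence intervals for planning. The only explicit significance level is two-sided 0.05, given in section 5.4.2.2 for overall survival. No section gives a gene-level alpha, a false discovery rate, a family-wise rule or a permutation reference.

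**The concern.** One pooled contrast over a fixed gene set needs no correction for 53 genes. Fifty-three separate contrasts do, if any of them is to be read as showing that a gene responds to propranolol. The plan includes both, attaches the word primary to the separate models, and does not rank the two. An analyst could follow the text and still choose, after seeing the data, whether the composite, the mixed model or a list of single genes is the main result, and at which draw.

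What is at stake is the finding that goes into the next trial. Genes picked out by chance come with exaggerated estimates, and this study is meant to inform later sample sizes. The genes are also co-regulated, so chance findings tend to arrive in groups. Several inflammatory or interferon genes moving together by chance would look like a pathway effect.

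**Working it through.** **The plan's own figure.** Section 5.2 enrols 40 to obtain 30 patients with complete gene data. It bases this on precedent and states no alpha, effect size, SD or power, so there is no power calculation to reproduce. The implied loss is 1 − 30/40 = 25%.

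**Inputs**
- Genes: 53. The symbols listed in 5.3.1, with ranges expanded, count to 19 inflammatory + 31 interferon + 3 antibody = 53.
- Draws: three. Baseline precedes treatment, so only Day −2 and Day +28 can show a drug effect.
- Analysed patients: 15 v 15. Section 5.2 aims for 30 in total, 15 of them on propranolol.
- Per-gene level: two-sided 0.05. This is assumed; it corresponds to the 95% intervals in 5.2.
- Correlation among genes: not given. I assume 0.4–0.6, in two structures: one common correlation across all 53 genes, or three mutually independent blocks of 19, 31 and 3.

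**Expected false positives if propranolol has no effect** (number of tests × 0.05, whatever the correlation)
- One draw: 53 × 0.05 = 2.65
- Two post-baseline draws: 106 × 0.05 = 5.3

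**Chance of at least one at a single draw, genes independent**
- 1 − 0.95^53 = 0.934

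**Correlated genes.** Simulation of 20,000 null trials per setting, 15 v 15, 53 t-tests at 0.05:

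| Correlation | Structure | At least 1 gene | 10 or more genes | Any gene after Benjamini-Hochberg at 5% |
|---|---|---|---|---|
| 0 | independent | 0.94 | 0.0002 | 0.05 |
| 0.4 | one block | 0.75 | 0.05 | 0.04 |
| 0.4 | three blocks | 0.82 | 0.03 | 0.05 |
| 0.6 | one block | 0.54 | 0.08 | 0.03 |
| 0.6 | three blocks | 0.69 | 0.06 | 0.04 |

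Correlation leaves the mean at about 2.65. It lowers the chance of any false positive but raises the chance of a large cluster: ten or more genes occur in about 3–8% of null trials, against roughly 0.02% under independence. Benjamini-Hochberg keeps the chance of any false discovery at 3–5% in every setting.

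**Price of correction.** At 15 per arm, the per-gene difference detectable with 80% power is 1.06 SD at 0.05. Under Bonferroni, 0.05/53 = 0.00094 per gene, it is 1.68 SD. Benjamini-Hochberg is less severe than Bonferroni, so 1.68 SD is the pessimistic end.

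**The case against.** The best reply is that 5.3.1 already contains the answer. It names the gene group as the final outcome and plans a composite and a mixed model, either of which reduces the 53 genes to one treatment contrast. This part stands: a reader might infer that the whole primary analysis is 53 unadjusted tests, and the text does not support that. It does not close the gap, because the primary label sits on the gene-by-gene models and nothing subordinates them to the pooled contrast.

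A second reply is that this is a pilot aimed at estimation. The gene models are said to quantify association, no gene-level alpha is stated, and nowhere does the plan say that it will declare single genes altered. This lowers the stakes, and it is why 0.05 is labelled as an assumption here. But 53 unadjusted 95% intervals would exclude zero about 2.65 times per draw by chance, and the plan calls these analyses primary.

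Two stronger readings should be set aside:
- One might count about 8 false positives over three draws (159 × 0.05 = 7.95). A third of those fall at baseline, where a difference cannot be a drug effect.
- One might take from section 5.2 that the team will judge the trial by how many genes are significant, because earlier studies "yielded hundreds of differentially expressed genes that generate statistically significant results in higher-order bioinformatics". That sentence is a precedent for the sample size. It places significance in the higher-order analysis, and a 53-gene set cannot yield hundreds of genes. It sets no decision rule.

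**Conclusion.** The concern holds in limited form. Section 5.3.1 plans a sound pooled analysis but does not make it decisive, does not settle which draw decides, and leaves the 53 gene-level results without false-discovery control. At an assumed two-sided 0.05, about 2.65 nominally significant genes per draw, or 5.3 over the two post-baseline draws, are expected with no drug effect. The chance of at least one at a draw is 93% under independence and about 55–82% at correlations of 0.4–0.6. Chance clusters of ten or more occur in about 3–8% of trials at those correlations. The expected counts depend only on the 0.05 level; the probabilities also depend on 15 v 15 and on correlation structures that the documents do not give.

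This should be changed before the stored samples are analysed. It does not invalidate the design, and the estimation purpose of the pilot moderates its weight.

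**What to change.** In section 5.3.1:
- Name one pooled contrast, either the composite or the mixed-model treatment effect, at Day +28 as the primary test. Section 5.1.2 already names that time point.
- State that the 53 gene-level models are supportive. Report Benjamini-Hochberg adjusted p-values across the 53 genes at each post-baseline draw, and call a gene altered only at a false discovery rate of 5%.
- Give unadjusted estimates with 95% intervals, marked as descriptive.
- Treat baseline comparisons as descriptive only.
- If a count of significant genes is reported, compare it with the distribution obtained by permuting arm labels over patients, which keeps the correlation among genes. Use all randomized patients with samples for this. Section 5.3.1 restricts the propranolol arm, but not the controls, to 80% adherence, so the filtered arms are no longer exchangeable by randomization and a permutation reference built on them would not be clean.

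The cost is a few sentences and a few lines of code, with no change to patients, samples or assays. The price is lower gene-level power, so fewer individual genes will be declared altered. A single pooled test at one draw needs no gene-level correction.

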2.4.3 Beta-blocker weaning

Beta-blocker will be weaned for one of three reasons: 1) completion of drug intervention (28 ± 2 days post-transplant), 2) intolerance secondary to side effects, or 3) onset of new medical symptoms rendering beta-blocker therapy as contraindicated (see section 2.3.2). For patients that are at 40 mg twice daily at the time of weaning, the dose will be reduced to 20 mg twice daily for one week before being discontinued entirely. For patients who are on 20 mg twice daily at the time of weaning, their dose will be stopped altogether.

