3.0 STUDY ENDPOINTS

3.1 Primary Endpoint

Expression levels of beta-adrenergic mediated gene expression will be compared between individuals randomized to propranolol vs. control just prior to HCT as well as 28 days following autologous HCT for MM. Quantification of whole genome RNA production will be performed with specific identification of expression of beta-adrenergic signaling pathways.

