3.2.2 Clinical

3.2.2.1 Feasibility

The feasibility portion of the study is the test of whether patients undergoing autologous HCT for MM can be placed and maintained on a beta-blocker during the immediate peri-transplant period. Feasibility to use propranolol in autologous MM HCT recipients for the adjunct cancer control purposes will be determined by a 55-70% enrollment rate and 65-70% retention rate as described below in sections 3.2.2.1a-b. The study intervention will be deemed feasible if both of the below parameters for enrollment and retention are met.

3.2.2.1a Enrollment rate

Based on similar biobehavioral cancer research efforts at other institutions, the target enrollment rate is 55-70%. Of all eligible patients that are approached, the goal is that 55-70% will provide informed consent and enroll in the study. This target rate also takes into account the possibility that enrollment may be slightly lower due to the present study being a drug intervention trial with potential patient reticence to enroll.

3.2.2.1b Retention rate

Based on similar research and the nature of drug intervention trials (as described in 3.2.2.1a), the target retention rate is 65-70%. Retention rate will be assessed individually for two time periods - prior to transplant (between Time 1 and Time 2) and from transplant through Day +30 (Time 2 to Time 3). This allows for assessing the impact on gene expression in both a run-in period preceding transplantation as well as during the transplant process, whereby there will be a greater number of confounding variables that may potentially impact gene expression and adherence. Participants will be considered to be retained in the study for the given time period assessment if they are 80% adherent to their prescribed dose of medication during the specified time period.

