Drug adherence will be measured as a percentage of the prescribed number of pills that were actually taken (either 20 mg or 40 mg twice daily). This will be determined outpatient via pill count on Day -2 and Day +28 and inpatient through nursing documentation. Patients will have one additional pill count upon return of the study supply of propranolol. The return will occur at the next earliest clinic appointment following discontinuation of the propranolol. There is no consensual standard for what constitutes adequate adherence. Clinical trials report average adherence rates of 43 to 78 percent among patients taking drugs for chronic conditions; some clinical trials define rates above 80% as acceptable.⁴³ A target adherence rate of 80% will be utilized in this study to constitute having adequately retained the patient in the study. Adherence will be recorded as a continuous (0-100%) variable. Adherence will be assessed separately during two time periods – prior to transplant (between Time 1 and Time 2) and from transplant through Day +28 (Time 2 to Time 3). Patients will be included in final analyses if and only if they have been adherent (at least 80% of the prescribed dose) to the study drug during the designated time period.

As the retention rate (participants' ability or inability to be maintained on the study drug) will necessarily be affected by side effects, we will collect side effect data to better

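### The primary gene-expression analysis sets only adherent propranolol patients against all controls, with no as-randomised comparison, although section 3.1 defines the endpoint by randomised group

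*Combined protocol and SAP*

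**What the plan says.** Section 3.1 states the primary endpoint as a contrast of the randomised arms: expression levels "will be compared between individuals randomized to propranolol vs. control just prior to HCT as well as 28 days following autologous HCT for MM".

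Section 5.3.1 analyses a different contrast. It models expression against use of the drug and then restricts one arm: "only gene expression data from study participants with an adherence rate of 80% (at either dose) will be used as comparators against the control group". The reason given is to secure adequate drug exposure. Section 3.2.2.1b repeats the rule for the final analyses, admitting patients "if and only if they have been adherent (at least 80% of the prescribed dose) to the study drug during the designated time period".

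On how adherence arises, the same section says: "Drug adherence will be measured as a percentage of the prescribed number of pills that were actually taken". It adds that retention "will necessarily be affected by side effects", and that in the transplant period "there will be a greater number of confounding variables that may potentially impact gene expression and adherence".

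Section 5.2 enrols 40 and aims for 30 with complete gene data, 15 of them in the intervention group, after attrition and intolerance. It describes the study's main product as effect sizes with 95% confidence intervals for planning later research.

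**The concern.** Adherence is determined after randomisation and is defined only by study-drug pills. The rule therefore removes patients from one arm, on a criterion that the protocol itself links to side effects and, after transplant, to factors that may also alter expression. Controls can drop out for want of a sample, but not for want of adherence. The arms that remain are no longer the randomised arms.

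If whatever lowers adherence also shifts inflammatory or interferon gene expression, the estimated difference mixes selection with drug effect. The confidence interval does not reflect that error. No randomised estimate is planned to set beside the filtered one, so a reader could not judge how much the filter mattered. Those who plan a later trial would carry forward an effect size whose meaning is unclear.

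**Working it through.** **1. The plan's own figures.** 30/40 = 15/20 = 0.75, an implied loss of 25%. Back again: 30/(1 − 0.25) = 40 and 15/(1 − 0.25) = 20. The figures agree with each other, but the 25% is inferred. The plan gives no alpha, power, effect size or attrition rate for this endpoint, so there is no formal calculation to reproduce.

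**2. How many patients the filter can remove (of 20 on propranolol).**
- Target of 15 in section 5.2: 20 − 15 = 5, a figure that also includes attrition.
- Retention target of 65-70% in section 3.2.2.1b: 20 × 0.65 = 13 and 20 × 0.70 = 14, so 7 or 6 removed.
- Controls removed on adherence: 0.

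**3. Is an as-randomised comparison given elsewhere?**
- Section 3.2.1.1 mentions treatment assignment, but for the secondary comparison by anxiety and depression.
- Section 5.3.1 has a comparison that disregards assignment, but it concerns unevenly distributed covariates.
- The ANCOVA in 5.3.1 and the adjusted estimates in 5.2 address imbalance between groups. Neither restores excluded patients.

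**4. Possible size of the bias (illustration).** The documents give no correlation between adherence and expression, so r = 0.2, 0.3 and 0.5 are assumed. The model has one composite score with SD 1, no drug effect, and latent adherence correlated r with the score. Of 20 propranolol patients, *a* are lost at random and then the *f* least adherent are removed. The test is a pooled two-sided t-test at an assumed 5%, with 200,000 runs per cell.

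Large-sample check: bias ≈ r × φ(z)/p, where p is the fraction kept and z = Φ⁻¹(p). For p = 0.75, φ(0.674)/0.75 = 0.318/0.75 = 0.424, which gives 0.085 SD at r = 0.2 and 0.212 SD at r = 0.5. The simulation for exactly 15 of 20 gives slightly less:

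| Propranolol v control | a / f | Bias in SD (r = 0.2, 0.3, 0.5) | Rejection rate, % |
|---|---|---|---|
| 15 v 15 | 0 / 5 | 0.080, 0.120, 0.202 | 5.6, 6.3, 9.0 |
| 15 v 15 | 2 / 3 | 0.056, 0.083, 0.141 | 5.3, 5.6, 7.0 |
| 15 v 15 | 3 / 2 | 0.041, 0.062, 0.104 | 5.2, 5.4, 6.1 |
| 15 v 15 | 5 / 0 | 0, 0, 0 | 5.0 |
| 14 v 15 | 0 / 6 | 0.094, 0.143, 0.239 | 5.8, 6.8, 10.1 |
| 13 v 15 | 0 / 7 | 0.110, 0.164, 0.274 | 5.9, 7.2, 11.4 |
| 14 v 20 | 0 / 6 | 0.095, 0.143, 0.239 | 5.8, 7.0, 10.6 |
| 13 v 20 | 0 / 7 | 0.110, 0.164, 0.274 | 6.1, 7.4, 12.1 |

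With r = 0 the rejection rate is 4.9-5.1% throughout. The sign of the bias depends on the sign of r, which is unknown. The mean 95% CI half-width is 0.69-0.77 SD, so every bias in the table is smaller than the half-width.

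**5. Who counts as adherent.** The denominator is the number of pills prescribed. The text does not say whether pills remain prescribed after an early stop. Over 28 post-transplant days, a patient who takes every dose and stops after day 10 scores 10/28 = 36% if all scheduled doses count, but 100% if counting ends at the stop. Counting all days does not exclude every early stopper either: 22/28 = 79% fails and 23/28 = 82% passes. Nor is it stated how the taper in section 2.4.3 enters when weaning comes early (from the higher dose, "the dose will be reduced to 20 mg twice daily for one week before being discontinued entirely").

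**6. Dilution in an as-randomised analysis.** In the worst case every excluded patient is sampled and shows no drug effect. The as-randomised effect is then 15/20 = 75% of the adherent effect, or 14/20 = 70% and 13/20 = 65% at the retention target.

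**The case against.** The strongest defence is that the filter is deliberate and openly explained. This is a small proof-of-concept study whose objective is the effect of giving the drug, and for a mechanistic question an exposure analysis is natural. An as-randomised contrast could lose 25-35% of the signal. That is a real cost and a good reason to keep the adherent comparison. It is not a reason to leave out the only comparison that randomisation protects.

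Several narrower points also have weight:
- Adherence is judged separately before and after transplant, so a patient who stops after transplant can still contribute at Day -2. The protocol expects most confounding after transplant, so the Day -2 contrast is less exposed. The illustration does not separate the periods.
- The baseline draw allows retained patients to be compared with controls before treatment. That can show selection on pre-existing expression, but not selection arising later.
- The denominator is partly settled. Adherence is counted at either dose level, and planned weaning starts around Day +28, so it hardly matters. The sense of retention also suggests that an intolerant patient counts as lost. The rule for early stops is still not written down.
- Section 4.4 schedules the draws without requiring that the patient be on drug, and section 2.4.2 continues outcome data after a stop. The samples may well exist, although research blood is not named.
- The correlations are assumed, and the largest figure (12.1%) needs r = 0.5, every loss due to the filter and no control losses. The last of these does not match the aim of 30 complete patients.

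These points limit the likely harm. None supplies a randomised estimate.

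**Conclusion.** The concern holds. The endpoint is defined by randomised arm, the stated primary analysis filters one arm on a post-randomisation criterion, and no as-randomised gene-expression comparison is specified. That much rests on the text alone.

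The size of the harm is not known from the documents. With assumed correlations of 0.2-0.5, the bias at 15 v 15 runs from zero (all losses are attrition) to 0.20 SD (all five due to the filter). At the retention target, with every loss due to the filter, the upper bound is 0.09-0.27 SD. These values are modest beside a CI half-width of about 0.7 SD, but the error would be systematic and the interval would not show it. The point should be corrected. It does not invalidate the design.

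**What to change.** Amend sections 5.3.1 and 3.2.2.1b as follows.

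1. Make the primary gene-expression comparison all randomised participants with an available sample, analysed as assigned, in line with 3.1.
2. Keep the comparison of patients at least 80% adherent as a labelled supportive (exposure) analysis, and limit the inclusion rule in 3.2.2.1b to that set.
3. State that the scheduled Day -2 and Day +28 research samples are still sought from patients who stop propranolol, except those who withdraw, for whom section 4.1 ends data collection.
4. For the supportive set, state whether doses after an early stop, a dose reduction or weaning count in the adherence denominator. This fixes membership of the set; it does not by itself exclude every early stopper.

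The cost is wording, plus draws already on the schedule from at most about 5-7 patients who are off drug. The statistical price is the dilution in step 6 of the working, and the adherent-only estimate remains available beside the primary one. No dose or clinical rule changes.

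### Covariates for the adjusted gene-expression comparison are picked by observed arm imbalance, with no threshold or candidate list, which is less precise than fixing prognostic covariates in advance

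*Combined protocol and SAP*

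**What the plan says.** Section 5.3.1 contains the only covariate rule for the arm comparison of gene expression. The sentence opens with "Any demographic or psychosocial variables (other than those of primary interest", closes that bracket, and says that those variables "that are unevenly distributed between groups after randomization will be adjusted for in subsequent analyses as previously described using ANCOVA". It does not say what counts as uneven (a test, a p-value or a standardised difference) or which variables are examined. No earlier part of the document describes an ANCOVA. Baseline expression is not named as a covariate, although blood is drawn at baseline (section 4.4).

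The next sentence of 5.3.1 adds a comparison of expression across any variables that may not have balanced, "to ascertain whether these differences may be stronger than drug-attributed changes".

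Section 5.2 promises two kinds of result: "We will generate both simple estimates of effect size as well as adjusted estimates". The purpose given there for the second kind is "attempting to control for any accidental confounding that may occur despite randomization". The section also says that the study is mainly meant to yield effect sizes and 95% confidence intervals for planning later work. It does not say which of the two estimates leads.

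**The concern.** Allocation is by permuted blocks with no stratification stated (section 4.1), so imbalance at randomisation is chance. Adjusting for a covariate improves precision when the covariate predicts the outcome, whether or not it is balanced. A rule keyed to imbalance can bring in variables unrelated to CTRA expression and leave out prognostic ones that happen to balance. Because uneven is undefined, two analysts could both follow the plan and report different adjusted effects.

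At stake is the adjusted effect size and its interval, which section 5.2 names among the study's main products. The follow-on comparison in 5.3.1 sets non-randomised contrasts against the drug effect with no common scale, test or decision rule, so it cannot show that one is stronger than the other.

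**Working it through.** **The plan's own figures.** Section 5.2: "We will enroll 40 participants undergoing autologous HCT for MM at MCW" and "we aim to have 30 patients with a complete set of gene data". 30/40 = 75%, an implied loss of 25%. The intervention arm is to supply 15, which leaves 30 − 15 = 15 controls. No alpha, effect size or SD is given for gene expression, so there is no power figure to reproduce.

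**Candidates (assumption).** Section 4.2 lists eight patient-related variables. Pre-diagnosis income is the SES measure (4.6.1, 5.4.1) and so presumably excluded as of primary interest. That leaves seven, or five if BMI and smoking are not counted as demographic. As the plan fixes none of this, one to ten candidates were tried.

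**How often the rule fires by chance.** For K independent variables and a test at level a, P(at least one uneven) = 1 − (1 − a)^K.
- K = 8: 34% (a = 0.05), 57% (0.10), 83% (0.20).
- K = 7: 30%, 52%, 79%.
- K = 10 with a standardised difference above 0.25: nearly every trial, about five variables on average (simulated).

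**Fixed adjustment, by formula.** Outcome SD 1, N = 30, k fixed normal covariates explaining R²:
SD of arm difference = √(2/15) × √(1 − R²) × √[(N − 3)/(N − 3 − k)].
- Unadjusted: √(2/15) = 0.365.
- Two prognostic, R² 0.25: 0.365 × 0.866 × √(27/25) = 0.329.
- All eight candidates, R² 0.25: 0.365 × 0.866 × √(27/19) = 0.377.
- Three non-prognostic: 0.365 × √(27/24) = 0.387.
- Baseline CTRA alone, assumed correlation 0.5: 0.365 × 0.866 × √(27/26) = 0.322.

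**The rule, by simulation.** Linear model, independent normal covariates, 15 per arm, 3,000 trials per cell; Monte Carlo error of each SD about 1.3%. One cell (eight candidates, two prognostic, R² 0.25, uneven = p < 0.10):

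| Estimator | SD | Mean 95% CI width |
|---|---|---|
| Unadjusted | 0.369 | 1.48 |
| Imbalance rule | 0.372 | 1.56 |
| Two prognostic, fixed | 0.333 | 1.33 |
| All eight, fixed | 0.382 | 1.55 |

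The simulated SDs for the other three estimators agree with the formula within about 1%. Here the rule's SD is 0.372/0.333 = 1.12 times that of fixed prognostic adjustment.

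**Rule against fixed prognostic covariates.** SD ratio over the settings run: 1.00 to 1.12 at R² 0.10, 1.01 to 1.17 at 0.25, 1.04 to 1.35 at 0.50. Ratios within 1–2% of 1.00 are ties.

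**Rule against no adjustment.** SD ratio with p < 0.10, as R² goes from 0 to 0.50:
- one candidate: 1.01 down to 0.89;
- five candidates: 1.05 down to 0.94;
- eight candidates, two prognostic: 1.07 down to 0.96.

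Over all triggers and settings the ratio ran from 0.73 to 1.15. With seven candidates and R² 0.30 it was 0.359/0.363 = 0.99.

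Mean interval width with significance-test triggers was larger than unadjusted for seven to ten candidates. With eight it was 1.56 against 1.48 (5% wider, the cell above). With ten at p < 0.10 it was 1.61 against 1.49 at R² 0.10 and 1.57 against 1.48 at R² 0.50. The exception was the loose 0.25 standardised-difference trigger at R² 0.50, where seven or eight candidates gave intervals about as wide as unadjusted or slightly narrower.

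**Error rates and power.** Coverage of the rule's intervals was 94–97%. With ten candidates, two prognostic, R² 0.30 and a true effect of 0.8 SD, power was 48–53% under the rule, 54–57% unadjusted and 67–69% with the two prognostic covariates fixed. Type I error under the rule was about 4%.

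**What a fixed set buys.** In that setting three fixed but non-prognostic covariates gave SD 0.38–0.39 and power 49–52%. Baseline CTRA at correlation 0.5 gave SD about 0.32 and power 65–68%.

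**The case against.** Several points on the other side stand.

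- A reader might infer that the rule is worse than not adjusting at all. That is not general: the SD comparison changes sign with the number of candidates and R², and the document gives neither.
- A reader might infer that the unadjusted result is lost or that false positives rise. Section 5.2 keeps the simple estimate, and the distortion in error rates is small and in the conservative direction.
- A reader might infer that disease and transplant factors are barred from the model. The sentence in 5.3.1 does not name them, but section 5.2 aims at any accidental confounding and 5.3.1 tabulates them, so exclusion is not established.
- The trigger looks at covariates, not outcomes, and samples are shipped together at study conclusion (4.4). Covariates could be chosen before expression data exist, but the plan does not require it.
- Fixing covariates is not automatically better. With eight candidates at R² 0.10, fixing all of them gave SD 0.413 against 0.387 under the rule. Nothing in the document shows that age, sex or BMI predicts CTRA expression, so there is no basis for insisting on that set.
- Restricting the propranolol arm to adherent patients (5.3.1) means that some imbalance in the analysed set may not be chance. That gives adjustment a further motive, but a rule with no threshold or list does not handle it reliably.

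What remains is that the selection criterion is wrong and undefined, and that it loses precision against a short prognostic set named in advance.

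**Conclusion.** The point holds in this form. The adjusted estimate that the plan offers for future planning is not defined in advance and depends on chance imbalance. At about 15 per arm and R² of 0.10 to 0.50, its SD exceeds that of pre-specified prognostic adjustment by under 1% to 35%. Inference is mildly conservative, so the cost is lost precision and power, not false positives. No general claim against the unadjusted analysis is supported, beyond wider intervals with seven to ten candidates under significance-test triggers.

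These sizes assume independent normal covariates, one composite outcome, chance imbalance only, and candidate counts and R² that the document does not supply. The figure for baseline CTRA also assumes a correlation of 0.5 with the later value and a baseline sample taken before the first dose. The change should be made; the trial's design does not depend on it.

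**What to change.** Replace the covariate sentence in 5.3.1 with:

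> The adjusted arm comparison of the CTRA composite at Day -2 and Day +28 uses ANCOVA with the participant's baseline CTRA value, plus at most one or two covariates named now for their expected relation to CTRA expression, kept whatever the observed balance. Baseline tables are descriptive and do not select covariates. The unadjusted estimate is reported alongside.

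The sponsor should choose and name the one or two further covariates. Label the comparison of covariate differences with drug-attributed changes as descriptive only.

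The cost is wording: baseline expression and the section 4.2 variables are already collected. The statistical price is one to three degrees of freedom and a small loss of precision if the chosen covariates prove non-prognostic. In the worst case of three such covariates, the formula gives SD 0.387 against 0.365 unadjusted, about 6% larger.
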